## **5.1 All Study Procedures**

The following evaluation and tests must be recorded as source documents of each patient.

### **5.1.1 Informed Consent**

Consent is obtained within 28 days before the enrollment in the observation period and subsequently, eligibility is confirmed.

### **5.1.2 Patient Background**

All the items of patient background information shown in [Table 5-1](#) are collected.

### **5.1.3 Patient enrollment**

Unique patient identification codes are assigned for screening at study sites and patient numbers are assigned by the time of enrollment in the observation period. At the time of enrollment in the treatment period, drug numbers are obtained. The allocation method is shown in Section [3.2](#).

### **5.1.4 Subjective and Objective Findings**

Subjective and objective findings are evaluated at the timing shown in [Table 5-2](#). The information regarding signs and symptoms observed at the time of enrollment in the treatment period is collected as the information regarding baseline signs and symptoms. All the abnormal findings considered to be clinically significant compared with baseline must be recorded as adverse events. The evaluation methods of adverse events shown in Section [12](#) are used.

### **5.1.5 Vital Signs**

As vital signs, blood pressure (systolic and diastolic), pulse rate and body temperature are measured at the timings shown in [Table 5-2](#). At all measurement timings, they should be measured keeping the patients at rest, using the same site and method in each patient.

The Investigator or Sub-investigator is responsible for assessing the changes in vital signs. If an abnormal result is obtained, measurement should be performed again immediately. Changes that are considered clinically significant based on the comparison with baseline must be recorded as adverse events. The evaluation methods of adverse events shown in Section [12](#) are used.

### **5.1.6 Compliance with treatment with study drugs**

Compliance with treatment with the study drugs is confirmed in every visit by checking the treatment diary and empty sheet of used study drugs, asking subjects questions and other methods from the start of the treatment with the study drugs to the completion of the treatment.

### **5.1.7 Concomitant medications and therapies**

The status of concomitant medications and therapies is confirmed and related information is collected at least in every visit by asking subjects questions or by other methods from the start of the treatment with the study drugs to the completion of the study participation period.

The information regarding all the concomitant medications (prescription drugs and over-the-counter drugs) and therapies is collected from the time of consent to the completion

of the study participation period and the status of their use is recorded in the source documents. The concomitant medications and therapies include the therapeutic agents used to treat adverse events or serious adverse events. For the concomitant medications and therapies for the adverse events the observation of the course of which is required at the time of the follow-up observation, information is collected until the completion of the observation of the course and the status of their use is recorded in the source documents. However, test agents, diagnostic agents or fluids for the administration of injections do not have to be recorded in the case report form (eCRF).

### **5.1.8 12-lead Electrocardiography**

Twelve-lead electrocardiography is performed at the timings shown in [Table 5-2](#). It should be performed keeping patients at rest, using the same method for each patient.

The Investigator or Sub-investigator is responsible for assessing the results of electrocardiography. All the abnormal findings considered to be clinically significant compared with baseline must be recorded as adverse events. The evaluation methods of adverse events shown in [Section 12](#) are used.

### **5.1.9 Laboratory Findings**

In laboratory tests, the items shown in [Table 5-1](#) are evaluated.

The Investigator or Sub-investigator must evaluate all the laboratory test values as to whether they are clinically significant events. When an event was considered to be a clinically significant event, its course must be observed as specified in the protocol and the event must be recorded as an adverse event. The evaluation methods of adverse events shown in [Section 12](#) are used. When liver damage is suspected, hepatic function tests are performed. When the tests showed  $\text{AST (GOT)} > 3 \times \text{ULN}$ ,  $\text{ALT (GPT)} > 3 \times \text{ULN}$  or  $\text{T-Bil} > 2 \times \text{ULN}$ , at least  $\text{AST (GOT)}$ ,  $\text{ALT (GPT)}$ , alkaline phosphatase (ALP) and T-Bil are tested once every 2 to 3 days and the condition of the patient is observed in detail.

#### **5.1.9.1 Hematology**

Blood samples for hematology will be collected at the time points shown in [Table 5-2](#).

#### **5.1.9.2 Serum chemistry**

Blood samples for serum chemistry will be collected at the time points shown in [Table 5-2](#).

#### **5.1.9.3 Urinalysis**

Urine samples for urinalysis will be collected at the time points shown in [Table 5-2](#).

### **5.1.10 Pregnancy Test**

Serum or urinary  $\beta$ -human chorionic gonadotropin is tested at the timings shown in [Table 5-2](#) in patients with childbearing potential to confirm that they are not pregnant. The test is unnecessary for patients without childbearing potential.

Note) Women without childbearing potential are those who underwent hysterectomy or postmenopausal women who did not have menstruation for 1 year or longer without medical reasons including use of contraceptive drugs.

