White blood cell count	Neutrophil	Eosinophil	Basophil
Lymphocyte	Monocyte	PT-INR	
Serum chemistry			
AST	ALT	ALP	BUN
Albumin	Creatinine	Na	Cl
K	T-Bil	Direct bilirubin	Total protein
CRP	CPK	LDH	γ-GTP
Blood sugar	Triglyceride	Total cholesterol	A/G
Urinalysis			
Protein	Occult blood	Glucose	Urobilinogen
Pregnancy test *4	Serum or urinary β-human chorionic gonadotropin		
Evaluation of symptom scores			
ICIQ-SF	PGI-I		
Evaluation of QOL score			
I-QOL			
Urination record			
Status of urinary incontinence, time and date	Presence or absence of pad change		
Urination time and date			
Pad test			
1-hour pad test			
Measurement of urinary flow			
Maximum urinary flow rate (free Q max )	Average urinary flow rate (free Q ave )		
Voided volume	Time of voiding		
Measurement of residual urine volume			
Evaluation of adverse events			

[figure not shown]
[figure not shown]
\*1: Automatically calculated from date of birth

\*2: Automatically calculated from height and body weight

\*3: Determined from the content of Q4 of ICIQ-SF

\*4: Required. When at least 1 year has passed after menopause or when the possibility of pregnancy is medically denied, the test is not necessary.

Table 2 Observation and Test Schedule

Timing	At enrollment in observation period	Observation period 	At enrollment in treatment period	Treatment period 				Follow-up observation 	At discontinuation 
				7 days before enrollment in treatment period	7 days before Week 4 visit	Week 4	7 days before Week 8 visit	Week 8	
Visit	1	2	3	4	5				
Week	-3		1			4		8	10 to 12
Acquisition of consent	X 								
Patient background survey	X		X						
Enrollment	X		X						
Study drugs	Prescription	X	X			X			
Collection of remaining drugs			X		X		X		X
Confirmation of compliance			X		X		X		X
Subjective and objective findings	X		X		X		X	X	X
Blood pressure, pulse rate and body temperature measurement	X 		X		X		X	X	X
12-lead electrocardiography	X 		X					X	X
Laboratory test 	X 		X		X		X	X	X
Pregnancy test 	X		X					X	X
Urination record	Distribution	X	X		X				
Collection			X		X		X		X
Confirmation of entry			X		X		X		X
Record of status of urinary incontinence									
Record of number of used pads									
Record of number of urinations									
1-hour pad test	X		X				X		X
ICIQ-SF evaluation	X		X		X		X		X
PGI-I evaluation			X		X		X		X
I-QOL evaluation			X		X		X		X

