Urinary flow test			X				X		X
Measurement of residual urine volume by ultrasonography	X 		X				X		X
Concomitant drugs and therapies 									X
Evaluation of adverse events 									X

1. Acquisition of consent: Consent is obtained within 28 days before the enrollment in the observation period.

2. Laboratory test: Hematological tests, serum chemistry and urinalysis are performed.

3. Pregnancy test: Required. When at least 1 year has passed after menopause or when the possibility of pregnancy is medically denied, the test is not necessary. The pregnancy test (serum or urine) before the enrollment must be negative.

4. Concomitant drugs/therapies, evaluation of adverse events: Investigated from the acquisition of consent to the completion of the follow-up observation period.
5. Acceptable range of observation period: Observation period is 3 weeks in principle, but up to 4 weeks is permitted.
6. Acceptable range of timings of visits in treatment period: Week 4 and Week 8 visits  $\pm$  3 days from the scheduled dates are permitted.
7. Follow-up observation: Observation is performed 2 to 4 weeks after the completion of Week 8 of the treatment period. When the treatment is discontinued, it is performed 2 to 4 weeks after the last administration of the study drugs.
8. In cases of discontinuation: Specified observation and tests are performed as much as possible.
9. When the specified observation and tests were performed within 14 days before the enrollment, even if it was before the consent, the results can be used as the data at the time of the enrollment in the observation period.

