(16) Pregnant or nursing women, or women of childbearing potential with positive pregnancy test (urine or serum) within 7 days before the enrollment in the treatment period

Note) Women without childbearing potential are those who underwent hysterectomy or postmenopausal women who did not have menstruation for 1 year or longer without medical reasons including use of contraceptive drugs.

(17) Other patients considered by the Investigator or Sub-investigator to be inappropriate as subjects of this study

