### 4.3 Patient Discontinuation Criteria

When patients meet the following conditions, administration of the study drugs is discontinued. Discontinuation criteria for individual patients are shown below.

- (1) When continuation of treatment is difficult because of onset of an adverse event
- (2) When the patient requested the withdrawal of consent
- (3) When a serious noncompliance with the study implementation procedures was noted
- (4) When continuation of the study became impossible due to a move, transfer to another hospital, busy schedule or other reasons of the patient
- (5) When a patient was found not to fulfill the criteria for subjects of this study (not meeting the inclusion criteria or meeting the exclusion criteria)
- (6) When the following liver damage for which a causal relationship with the study drugs of this study cannot be denied occurred
  - 1) AST (glutamic oxaloacetic transaminase [GOT]) or ALT (glutamic pyruvic transaminase [GPT]) > 8 × ULN
  - 2) AST (GOT) or ALT (GPT) > 5 × ULN persisting for 2 weeks or longer
  - 3) AST (GOT) or ALT (GPT) > 3 × ULN with total bilirubin (T-Bil) > 2 × ULN or international normalized ratio (INR) > 1.5
  - 4) AST (GOT) or ALT (GPT) > 3 × ULN and onset of malaise, nausea, vomiting,

right upper quadrant pain/tenderness, pyrexia, rash or eosinophilia (> 5%)

- (7) When a patient became pregnant
- (8) When the effect of the study drugs was insufficient or symptoms were exacerbated and the Investigator or Sub-investigator considered that the study should be discontinued
- (9) Other cases in which the Investigator or Sub-investigator considered the discontinuation of the study necessary

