### **5.1.17 Evaluation of Adverse Events**

As shown in [Table 5-2](#), it is checked whether there are untoward medical occurrences (adverse events or serious adverse events) including adverse reactions on each day of visit from the time of consent to the completion of study participation period. The evaluation methods of adverse events shown in [Section 12](#) are used.

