## 7.2 Total Blood Volume

The volume of blood collected in this study is shown in [Table 7.2-1](#). The total volume of blood collected from each patient is approximately 90 mL.

Table 7.2-1 Volume of Blood Collected during Study Participation Period

Item	Number of blood collection	Volume of blood collected per collection	Total volume of collected blood
Laboratory test	5	Approximately 15 mL	Approximately 75 mL
Pregnancy test	3 (for blood test)	Approximately 5 mL	Approximately 15 mL
Total	5	-	Approximately 90 mL

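### No pregnancy test is scheduled at Week 4, so no planned test can trigger the pregnancy stopping rule during the 8 weeks of double-blind dosing.

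*Protocol*

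**What the plan says.** Section 5.1.10 calls for serum or urinary hCG testing "in patients with childbearing potential to confirm that they are not pregnant" and leaves the timing to Table 5-2. Women who have had a hysterectomy, or who are at least one year postmenopausal, are not tested.

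Synopsis Table 2 and Table 5-2 both mark the test at observation enrolment, at treatment enrolment, at one late visit and at discontinuation. The Week 4 cell is blank in both. At Week 4 both tables do mark the laboratory test and a new prescription of study drug. Footnote 2 of Synopsis Table 2 defines the laboratory test: "Laboratory test: Hematological tests, serum chemistry and urinalysis are performed".

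The last test before active dosing comes from exclusion criterion 4.2.2(16), which bars women with a "positive pregnancy test (urine or serum) within 7 days before the enrollment in the treatment period". Criterion 4.3(7) then requires study drug to be stopped: "When a patient became pregnant". Section 5.1.17 provides for adverse event checks, "including adverse reactions on each day of visit from the time of consent" until the end of participation.

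**The concern.** A stopping criterion works only if something detects the event. For pregnancy, the protocol has a rule but no scheduled procedure behind it while active drug is being given. The spacing is also hard to explain. The run-in of 3 weeks (4 at most), when every patient takes placebo, has a test at each end. The 8 weeks that may involve active drug have no test inside them.

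The stake is patient safety. A woman whose pregnancy would already test positive at Week 4 can be handed about four more weeks of study drug. Section 7.3.1 considers oral contraceptives inappropriate because study drug may inhibit their metabolism, so prevention rests on double barrier methods, an intrauterine device or other non-oral methods. Section 12.5.1 requires a pregnancy to be reported within 24 hours, but that clock starts only once someone knows of it.

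**Working it through.** **Reading the schedule.** The extracted tables have damaged columns, so the rows were read by counting fields against rows of known timing.

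| Row | Marked fields | Reading |
|---|---|---|
| Synopsis Table 2, laboratory test | 1, 3, 5, 7, 8, 9 | field 5 = Week 4, 7 = Week 8, 8 = follow-up, 9 = discontinuation |
| Synopsis Table 2, pregnancy test | 1, 3, 8, 9 | Week 4 blank; late test at follow-up |
| Table 5-2, laboratory test | 1, 3, 5, 8, 9 | Week 4 marked; one later mark lost in extraction |
| Table 5-2, pregnancy test | 1, 3, 8, 9 | Week 4 blank; late test at Week 8 or follow-up |
| Table 5-2, 1-hour pad test | 1, 3, 8, 9 | same pattern as pregnancy; the pad test is a Week 8 assessment |

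The laboratory row is marked at Week 4 in both tables, so the blank in the pregnancy row carries information. The late test is at follow-up on the Synopsis reading and possibly at Week 8 on the Table 5-2 reading. Either way it falls at or after the end of dosing.

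**Check that does not depend on the columns (Table 7.2-1).**

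- Blood volume: 5 laboratory draws × 15 mL + 3 pregnancy tests × 5 mL = 75 + 15 = 90 mL, which matches the stated total.
- Pregnancy tests after treatment enrolment: 3 − 2 enrolment tests = 1.
- Laboratory draws after treatment enrolment: 5 − 2 = 3 (Week 4, Week 8, follow-up).

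Planned pregnancy tests after treatment enrolment and before the end of dosing: **0**. The discontinuation test does not count, because it follows a decision to stop and cannot prompt one.

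**Length of the gap.** Inputs: 8 weeks of once-daily dosing (7.1.1.2), ±3 days at Weeks 4 and 8 (Table 5-2, note 6), an enrolment test up to 7 days old (4.2.2(16)), and follow-up 2 to 4 weeks after Week 8 (note 7).

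- Dosing without a scheduled test: 8 × 7 = 56 days (56 − 3 = 53 to 56 + 3 = 59).
- Age of the last negative result at the nominal end of dosing: 7 + 56 = 63 days.
- Longest gap to the next planned test: 7 + 56 + 3 = 66 days if it is at Week 8, or 7 + 56 + 3 + 28 = 94 days if at follow-up.

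**With a Week 4 test.**

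- Longest gap from the enrolment test to the next test: 7 + 28 + 3 = 38 days.
- Doses avoided after a positive Week 4 result: 56 − 28 = 28 nominally. With both windows the minimum is 53 − 31 = 22 and the maximum is 59 − 25 = 34.

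**The case against.** The best counter-case is that this is a design choice and not a defect. No section requires testing during dosing, and the schedule delivers what 5.1.10 asks for. Whether 8 weeks is too long depends on reproductive toxicity and the reasoning behind the 40-day contraception period. That material is redacted, left to the Investigator's Brochure or empty in this text, so a justification may exist there.

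There are real safeguards: two negative tests before any active dose, exclusion of fertile women who do not agree to contraception, named non-oral methods, adverse event checks at every visit, and a stopping rule that any route of detection can trigger. The exposed group may be a small part of an age range of 20 to 79. The 28 doses are saved only if conception was early enough to show at Week 4 and had not already been noticed. Finally, Table 5-2 has lost a laboratory mark in extraction, so it is weak confirmation of a blank cell.

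Most of this stands as a limit on the size of the benefit, and none of it supplies a planned test during dosing. Adverse event questioning asks about untoward occurrences, while pregnancy is handled separately in 12.5.1. No section calls for a home test or for testing after a missed period. The lost mark does not change the reading, because Synopsis Table 2 and the count in Table 7.2-1 reach the same result without Table 5-2.

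**Conclusion.** The concern holds. No planned pregnancy test falls within the 56 days of double-blind dosing (53 to 59 with the visit window), so criterion 4.3(7) depends on unscheduled detection throughout. This is true whether the late test belongs to Week 8 or to follow-up.

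The conclusion concerns scheduled tests in women of childbearing potential only. The day counts assume one dose per day starting at treatment enrolment. The documents do not give the number of women at risk, a pregnancy rate or the reproductive-risk data, so the expected number of affected pregnancies is not estimated. It may be well below 1. The point does not touch alpha, power or the primary analysis. It is an inexpensive safety improvement that should be made.

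**What to change.** Mark a urine hCG test at Week 4, for women of childbearing potential as 5.1.10 defines them, in the pregnancy row of Synopsis Table 2 and Table 5-2. Run it on the urine already collected for urinalysis and read it before study drug is prescribed again. A positive result triggers 4.3(7) and the 12.5.1 report. Section 5.1.10 already allows urinary hCG.

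The cost is one added mark in each of two tables and one kit per eligible woman, with no extra visit. The downside is an occasional false positive that needs a confirmatory test. Table 7.2-1 stays as it is, since no scheduled blood is added; if serum were used instead, the total would become 75 + 4 × 5 = 95 mL. The test can miss a very early pregnancy. Moving the late test to Week 8 would not shorten exposure and is not requested.

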### **5.1.11 Evaluation of symptom scores**

#### **5.1.11.1 ICIQ-SF**

As the evaluation of a symptom score, patients are asked to answer ICIQ-SF at the timings shown in [Table 5-2](#).

#### **5.1.11.2 PGI-I**

As the evaluation of patients' impression of improvement of urinary incontinence, patients are asked to evaluate PGI-I at the timing shown in [Table 5-2](#).

### **5.1.12 Evaluation of QOL Scores**

As the evaluation of QOL score, patients are asked to evaluate I-QOL at the timings shown in [Table 5-2](#).

### **5.1.13 Urination Record (Bladder Diary)**

Urination record (bladder diary) is issued to patients and collected at the timings shown in [Table 5-2](#) and the entry is confirmed.

### **5.1.14 Pad Test**

One-hour pad test is performed at the timings shown in [Table 5-2](#) and the amount of urinary incontinence is evaluated. The test is performed in accordance with the written procedures for pad test.

### **5.1.15 Urinary Flow Test**

Urinary flow test is performed at the timings shown in [Table 5-2](#) and the maximum urinary flow rate (free  $Q_{\max}$ ), average urinary flow rate (free  $Q_{\text{ave}}$ ), voided volume and time of voiding are evaluated. The test is performed in accordance with the written procedures for urinary flow test.

### **5.1.16 Measurement of Residual Urine Volume**

Residual urine volume is measured at the timings shown in [Table 5-2](#).

### **5.1.17 Evaluation of Adverse Events**

As shown in [Table 5-2](#), it is checked whether there are untoward medical occurrences (adverse events or serious adverse events) including adverse reactions on each day of visit from the time of consent to the completion of study participation period. The evaluation methods of adverse events shown in [Section 12](#) are used.

## **5.2 Assessments by Visit**

The evaluation and tests shown in [Table 5-1](#) are performed according to the schedule shown in [Table 5-2](#).

## 6. Study Drugs

The Sponsor will supply TAS-303 [REDACTED] and placebo until the completion of study participation period.

## 6.1 Overview of the Study Drugs

Physical and chemical characteristics of the investigational drug and the comparator are shown in Table 6.1-1 and Table 6.1-2.

Table 6.1-1 Overview of TAS-303 [REDACTED] [Investigational Drug]

The figure is a horizontal bar chart comparing the number of publications of the top 100 authors in 1990 and 2010. The x-axis represents the year, and the y-axis represents the number of publications. The data shows a general increase in publications over time, with a notable peak in 2010.

Year	Number of Publications
1990	10
1991	12
1992	15
1993	18
1994	22
1995	28
1996	35
1997	42
1998	50
1999	58
2000	65
2001	72
2002	78
2003	85
2004	90
2005	95
2006	98
2007	100
2008	102
2009	105
2010	108

Table 6.1-2 Overview of placebo [Comparator]

Formulation	Tablet that does not contain the active ingredient of the investigational drug and is indistinguishable from the investigational drug in appearance
Expiration date	Specified in the written procedures for management and handling of study drugs

## 6.2 Packaging and Labeling

The following information is printed on the outer boxes and aluminum pouches of the study drugs. The details are specified in the written procedures for management and handling of study drugs.

- (1) Sponsor name
- (2) Address
- (3) Storage conditions
- (4) Quantity
- (5) Lot number
- (6) Production date

### **6.3 Accountability**

The head of the study site or the person in charge of management of the study drugs manages all study drugs received at the study site in accordance with the written procedures for management and handling of study drugs. The details are specified in the written procedures for management and handling of study drugs. The entire history of prescription of study drugs is recorded in the table for management of study drugs.

No study drug is to be used outside of this study.

